- The milk load(s) will be administered after the overnight fast.
- At least one week will be allowed between each test in the same volunteer.

The following milk type will be randomly administered to the volunteers:

1. Human natural milk
2. Cow natural milk
3. A low-protein, cow-derived milk, similar to the human one for total protein content, but with a casein-to-whey protein ratio of casein typical of human milk (20:80);
4. A high-protein, cow-derived milk, similar to natural cow milk for total protein content, but with a casein-to-whey protein ratio of casein typical of human milk (20:80);

All milk loads will contain the same lactose amount (0.36 g/kg BW)

The human milk, whenever available, will be furnished by the Milk bank of the Dept. of Pediatrics of Padova University Hospital or by other available official Milk banks [...].

All modified milk types will be handled and prepared under proper aseptic conditions.

Study protocol (see also the attached scheme)

The volunteers were admitted to the clinical study unit at 08:00 after the overnight fast. A 20-g cannula was inserted in an antecubital vein for blood withdrawal. After two baseline samples spaced by \approx 10', the milk load was administered over 2'-5' to the volunteers. Starting from the end of milk ingestion ($t = 0'$), blood samples were taken at min 5', 10', 20', 30', 60', 90', 120', 180', and 240', then immediately transferred to two series of plastic tubes, containing either Na-EDTA (6% w/vol), for glucose, amino acid, insulin and C-peptide determinations, or a protease inhibitor (EMD Millipore Corporation, Merck KGaA, Darmstadt, Germany), for GIP and GLP-1 assay [...]

Key References:

2. Hartmann R and Meisel H. Food-derived peptides with biological activity: from research to food applications. *Current Opinion in Biotechnology* 2007, 18:163–169.

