Effects of the ingestion of human, cow and modified cow milk, on glucose, amino acid and hormone responses in humans

Acronym: PROLAT

Statistical analysis

The statistical analysis was performed either on data absolute values, or as relative changes vs baseline. The incremental area(s) under the curve (iAUC) within specific time intervals were calculated using the trapezoidal approach. The one Way ANOVA was applied to analyze one single set of data in the four experimental groups, followed by post-hoc analysis using the Fisher's test. With multiple measurements over time, the data were analyzed using the two-Way Analysis of Variance (ANOVA) for repeated measurements, followed by the post-hoc Fisher's test. The two tailed Student's t test for unpaired data was used in some instances for head-to-head comparisons, as specifically indicated. The Statistica® Software (version 10) program was employed. A p value equal or less than 0.05 was considered statistically significant. Power analysis, sufficient to detect a ≈30% difference between two means, with a RMSSE (Root Mean Standardized Square Error) of <0.5, a power of 80%, and a two-sided level of significance of 0.05%, indicated a sample size of at least 29 subjects.

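### The protocol allows repeat tests in one volunteer, but the SAP's one-way ANOVA and unpaired t tests have no volunteer term; where milks share volunteers and responses correlate, these tests are conservative

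*SAP*

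**What the plan says.** **Protocol, Experimental design.** Four milks are given at random: "The following milk type will be randomly administered to the volunteers". The plan speaks of one or more loads ("The milk load(s) will be administered after the overnight fast") and sets a minimum gap: "At least one week will be allowed between each test in the same volunteer". It gives no number of milks per volunteer, no sequence and no allocation ratio. The protocol is labelled an extract and refers to an attached scheme that is not in the text supplied.

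**SAP, Statistical analysis.** Three tests are named:

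- For single sets of data (presumably including each iAUC): "The one Way ANOVA was applied to analyze one single set of data in the four experimental groups", followed by Fisher's post-hoc test.
- For measurements over time: "two-Way Analysis of Variance (ANOVA) for repeated measurements", again followed by Fisher's test.
- For some comparisons: a "t test for unpaired data was used in some instances for head-to-head comparisons". The SAP says these instances are marked where they occur.

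No paired test is named, and no volunteer, period or sequence term. The power statement "indicated a sample size of at least 29 subjects", without saying whether this is a total or a number per milk.

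**The concern.** A minimum gap between tests in one person has a purpose only if some people are tested more than once. One-way ANOVA and the unpaired t test treat every value as coming from a different person. If the same person supplies values for two milks being compared, and those values are positively correlated, part of the person-to-person variation cancels from the difference. Neither test takes that into account. The Fisher comparisons after the one-way ANOVA use its error term and share the fault.

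The study's aims are comparisons of responses between milks. A finding of no difference, for instance between human milk and a modified cow milk, could then reflect the test rather than the milks.

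**Working it through.** **1. The plan's own figure.** The power statement works "with a RMSSE (Root Mean Standardized Square Error) of <0.5" and 80% power. With noncentrality n(k−1)RMSSE², RMSSE = 0.5 and two-sided 0.05, four groups need 16 each (64 in total) and two groups need 33 each (66). So 29 is not reproduced. RMSSE is only bounded and no SD is given, so this does not show 29 to be wrong. It is used below only as a convenient number of volunteers.

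**2. The texts side by side.** The protocol provides for repeat tests. The SAP's only repeated-measures method is tied to time, and the SAP does not say whether milk is a between- or within-volunteer factor in it. Single-value outcomes go to tests with no volunteer term. The texts fit together only if no comparison shares volunteers, and neither says so.

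**3. Standard error.** Let n be the number per milk, σ the total SD, q the share of volunteers common to the two milks, and ρ the within-volunteer correlation of the analysed response. Neither q nor ρ is in the documents.

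- True variance of a milk difference: 2σ²(1−qρ)/n.
- Variance assumed by the unpaired test: 2σ²/n.
- Ratio of assumed to true standard error: 1/√(1−qρ).

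With q = 1 and ρ = 0.3 / 0.5 / 0.7, the ratio is 1/√0.7 = 1.20, 1/√0.5 = 1.41 and 1/√0.3 = 1.83. For the one-way F test under no difference, the between-milk mean square has expectation σ²(1−ρ) but is divided by one with expectation σ².

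**4. Size and power.** Assumed: 29 volunteers all taking four milks, normal data with equal correlation, nominal two-sided 5%, and means (d, 0, 0, 0) with d = 0.5 SD. The size of both tests and the power of the one-way F come from 100,000 simulated data sets per setting, except at ρ = 0, where the size is 5% by theory. The F test with volunteer modelled (no period term, df 3 and 84) has noncentrality 29 × 0.75 × d²/(1−ρ). At d = 0.5 this is 5.44/(1−ρ), which is 7.77 / 10.88 / 18.13 at ρ = 0.3 / 0.5 / 0.7.

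| Assumed ρ | 0 | 0.1 | 0.3 | 0.5 | 0.7 |
|---|---|---|---|---|---|
| True size, unpaired t (%) | 5 | 3.9 | 2.0 | 0.7 | 0.1 |
| True size, one-way F (%) | 5 | 3.5 | 1.2 | 0.2 | <0.1 |
| Power, one-way F (%) | 46 | 44 | 40 | 35 | 28 |
| Power, F with volunteer (%) | 46 | 50 | 62 | 78 | 95 |

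Repeat runs differ by about 0.1 percentage point in size and 1 point in power. Fitting period as well gives 59 / 76 / 94% at ρ = 0.3 / 0.5 / 0.7. For one milk against another at 0.5 SD, the unpaired t test has 46 / 45 / 44% power, against 59 / 74 / 92% for a paired test.

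**5. What reduces the effect.**

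- *Partial overlap.* With q = 0.5 and ρ = 0.3 / 0.5 / 0.7, the ratio falls to 1.08 / 1.15 / 1.24. The size, approximately 2Φ(−1.96 × ratio), is 3.4 / 2.4 / 1.5%.
- *Large effects.* For this pattern of means, RMSSE = √(0.75d²/3) = d/2. So d = 0.5 is RMSSE 0.25, and the SAP's bound of 0.5 is d = 1.0. At d = 1.0 both F tests have at least 98% power at every ρ in the table, and the gap is under 1 point.
- *Low correlation.* At ρ = 0 there is no loss, and at 0.1 it is about 6 points at 0.5 SD.

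**The case against.** The strongest reply is that the documents show no error. The protocol is an extract, and the missing scheme is a natural place for the allocation, so its absence here does not mean the plan lacks it. The SAP's reference to groups and to unpaired data is consistent with separate groups of people. The unpaired tests are confined to marked instances and may have been kept for comparisons between different volunteers. Even a volunteer who took several milks does no harm to an unpaired comparison of two milks that have nobody in common.

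The reply goes on that the error, if present, is in the cautious direction, so significant milk differences are not undermined. The size rests on assumed overlap, correlation and effect. The SAP also analyses changes from baseline and incremental areas. Baseline adjustment removes stable differences in level between people, so the relevant correlation may be lower than for absolute values.

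All of this stands and limits the claim. It does not remove it. The protocol's spacing rule concerns tests in one person, and the SAP has no term for that person outside the time courses. The repeated-measures ANOVA does not fill the gap for single-value outcomes. For the time courses, not saying how milk enters is a gap in wording, not a demonstrated fault.

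**Conclusion.** The concern holds conditionally. Where the milks compared share volunteers and the within-volunteer correlation of the analysed response is positive, the one-way ANOVA and unpaired t tests overstate the standard error of milk differences and are conservative. With full overlap and correlations of 0.3 to 0.7, a nominal 5% test runs at about 2% down to 0.1% or less. At 0.5 SD, the power lost on the overall F test is about 22 to 67 points (62 − 40 and 95 − 28). These are illustrations, because overlap, correlation and effect size are all assumed. The loss is smaller with partial overlap or low correlation and almost nil at 1 SD. With one milk each, no shared volunteers in a comparison, or zero correlation, there is no error.

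A reader might infer two stronger things. One is that this was a full crossover analysed wrongly. The text supplied gives no number of milks per volunteer, so that is not established. The other is that the tests produce false positives. That could happen if one volunteer supplied several values to the same side of a comparison, but no pooled comparison is described. The point merits correction because the two texts need reconciling and the remedy is cheap; confidence is medium because the allocation is not visible.

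**What to change.** 1. Reconcile the protocol and the SAP: state how many milks each volunteer took, in what order, and which comparisons (including those made by unpaired t test) share volunteers.
2. Wherever milks share volunteers, replace the one-way ANOVA and unpaired t tests by a linear mixed model with milk and period as fixed effects and volunteer as a random effect. Take head-to-head comparisons as contrasts from it. The model also handles volunteers who took only some of the milks, which may matter because the protocol makes human milk subject to availability.
3. On the same condition, treat milk as a within-volunteer factor in the time-course analysis.
4. Where no volunteers are shared, say so and keep the present tests.

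The cost is SAP wording and a re-analysis of existing data, with no new volunteers or samples. A few degrees of freedom go to volunteer and period. If the correlation is zero, about 1 to 2 points of power are lost. In simulation with one milk 0.707 SD from the rest (an assumed effect), the overall F test had 77% against 78% power with all four milks each, and 40% against 42% with two of the four each.
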